## 7.8 *N. americanus* Donor Sub-Study

Transition to and enrollment into the Donor Sub-Study of protocol SVI-CH-01 will be scheduled at or before Study Day 280. In this sub-study participants will agree to continue being infected with *N. americanus* and to provide routinely scheduled fecal samples of not more than three per month. Participants will not receive the 3-dose treatment of albendazole 400 mg scheduled at Study Day 280, but will be permitted to remain infected initially for up to 6 years. During the donor sub-study, participants will be tested for infection with HIV and viral hepatitis (B and C) when they provide a fecal sample that may be used to prepare larvae for application to human study subjects, if this testing has not been done in the previous 30 days. If any participant in the donor sub-study develops new infection with HIV, hepatitis B or hepatitis C, they will be withdrawn from the sub-study and provided treatment for the *N. americanus* infection as described in the protocol for study SVI-CH-01.

Study participants who enroll into the Donor Sub-Study of protocol SVI-CH-01 will remain as participants in protocol SVI-CH-02/DMID 16-0116 until Visit #39 as described above. Participants will complete all study procedures described in Sections 7.3 and 7.4 and will be considered to have completed protocol SVI-CH-02/DMID 16-0116 after Visit #39 (study day 380) is completed.

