#### **2.3.2 Precautions Taken to Minimize Risks**

In order to minimize the risk to subjects, all subjects will be monitored closely during their participation in this study. The study vaccines, AP 10-701, and CpG 10104 have been produced according to current Good Manufacturing Practices (GMP). The *N. americanus* larvae that will be used in this study have been produced according to the procedure outlined in the IND for this product. The vaccine products and *N. americanus* larvae will be administered by experienced investigators with drugs and equipment available for the treatment of anaphylaxis and other potential adverse reactions. All vaccine doses will be given by intramuscular injection to minimize injection site reactions such as pain.

Subjects will be monitored throughout their infection for the development of anemia, by means of regular complete blood counts. Any subject who develops significant anemia during the study

that meets one of the halting rules (see **Section 9.5**) will be treated with albendazole for the infection, according to the procedure outlined in **Section 7.7** of the protocol.

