#### Safety

The following parameters will be evaluated for each formulation of Na-GST-1, in comparison to the saline placebo control:

1. Frequency of solicited injection site and systemic reactogenicity, graded by severity, on the day of each study vaccination through 14 days after each study vaccination.
2. Frequency of solicited adverse events, graded by severity, on the day of CHHI through study Day 280.
3. Frequency of study vaccine-related Serious Adverse Events from the time of the first study vaccination through approximately 10 months after the last study vaccination.
4. Frequency of clinical safety laboratory adverse events.
5. Frequency of unsolicited adverse events, graded by severity, from the time of each study vaccination through approximately 1 month after each study vaccination; and from the time of CHHI through treatment with albendazole (Day 297).
6. Frequency of new-onset chronic medical conditions through approximately 10 months after the third study vaccination.
7. Frequency of Adverse Events of Special Interest through approximately 10 months after the third study vaccination.

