2. Record vital signs.
3. Obtain fecal sample for parasitological testing.
4. Collect prior weeks' GI symptom memory aids and give two new weekly GI symptom memory aids.
5. Obtain blood for hematology.

Study Day 252 (Visit #30) – Telephone Call

1. Review interim medical history emphasizing any acute signs or symptoms (including entries on the GI symptom memory aid).
2. Collect concomitant medication information.

Study Day 259 (Visit #31)

1. Perform basic history and physical exam, emphasizing examination of any acute complaints.
2. Record vital signs.
3. Obtain fecal sample for parasitological testing.
4. Collect prior weeks' GI symptom memory aid and give two new weekly GI symptom memory aids.
5. Obtain blood for hematology.

Study Day 266 (Visit #32) – Telephone Call

1. Review interim medical history emphasizing any acute signs or symptoms (including entries on the GI symptom memory aid).
2. Collect concomitant medication information.

Study Day 273 (Visit #33)

1. Perform basic history and physical exam, emphasizing examination of any acute complaints.
2. Record vital signs.
3. Obtain fecal sample for parasitological testing.
4. Collect prior weeks' GI symptom memory aid and give new weekly GI symptom memory aid.

Study Day 280 (Visit #34)

1. Perform basic history and physical exam, emphasizing examination of any acute complaints.
2. Record vital signs.
3. Obtain fecal sample for parasitological testing.
4. Collect prior week's weekly GI symptom memory aid.
5. Obtain blood for hematology, antibody and cellular assays.
6. For females, obtain a urine sample for pregnancy testing. Test must be negative to proceed with albendazole administration.

7. Dispense 3-dose treatment of albendazole 400 mg once a day by mouth.
8. Observe administration of 1st dose of albendazole, and provide 2 remaining doses to subject for at-home use.

Study Day 290 (Visit #35)

1. Obtain fecal sample #1 collected approximately 1 week post-treatment with albendazole, for test of cure.

Study Day 294 (Visit #36)

1. Obtain fecal sample #2 collected approximately 1.5 weeks post-treatment with albendazole, for test of cure.

Study Day 297 (Visit #37)

1. Obtain fecal sample #3 collected approximately 2 weeks post-treatment with albendazole, for test of cure.
2. Obtain blood for antibody and cellular assays.

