### 8.2 Laboratory Evaluations

#### 8.2.1 Clinical Laboratory Evaluations

Using standard techniques, the tests listed below will be performed at the site's clinical laboratory. One or more of the laboratory parameters may be repeated at any time during the

study as determined by the PI, if indicated by an AE. A clinically significant abnormal value should be repeated within 10 days if possible and followed up as clinically relevant.

1. Complete blood count plus white blood cell (WBC) differential\*
2. Serum creatinine
3. Alanine aminotransferase (ALT)
4. Rheumatoid factor (RF)
5. Anti-double stranded DNA antibody (anti-dsDNA)
6. HBsAg ELISA
7. HCV serology
8. HIV serology
9. Serum ferritin

*\*The following CBC parameters will be assessed for safety throughout the trial: WBC count, absolute neutrophil count, absolute eosinophil count, hemoglobin concentration and platelet count.*

Urine pregnancy testing will be performed at the clinical trial site using test kits that have been approved by the FDA. Urine dipstick testing will also be performed at the trial site using an approved product.

Parasitological and immunology assays (see below) will be performed in the laboratories of the Department of MITM at the GWU, and at Baylor College of Medicine (fecal PCR for hookworm DNA).

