## 9 ASSESSMENT OF SAFETY

### 9.1 Specification of Safety Parameters

Safety will be assessed by the frequency and severity of:

1. Study product (vaccine or CHHI)-related serious adverse events occurring from the time of the first study vaccination through approximately 10 months after the last study vaccination.
2. Study vaccine-related solicited Adverse Events – reactogenicity events occurring on the day of each study vaccination through 14 days after each study vaccination:
  - a) Injection site reactions including erythema (redness), induration (hardness)/swelling, pain, and tenderness.
  - b) Systemic reactions including fever, myalgia (body aches/muscular pain exclusive of the injection site), arthralgia (joint pain exclusive of the injection site), headache, nausea, and vomiting.
3. CHHI-related solicited adverse events – reactogenicity events occurring on the day of CHHI through study Day 280 (time of treatment with first dose of albendazole):
  - a) Application site reactions including pruritus, rash, induration (hardness)/swelling, pain, and tenderness.
  - b) Gastrointestinal reactions including abdominal pain, abdominal bloating, flatulence, nausea, vomiting, and diarrhea.
  - c) Respiratory reactions (possibly due to migration of larvae through the lungs) including cough and sore throat.
4. Clinical safety laboratory adverse events occurring throughout the study. Parameters to be evaluated include WBC, ANC, absolute eosinophil count, hemoglobin concentration, and platelet count; ALT; creatinine; rheumatoid factor; and, anti-ds DNA antibodies.
5. Unsolicited Adverse Events – non-serious adverse events occurring from the time of each study vaccination through approximately 28 days after each vaccination and from study Day 140 (day of CHHI) through Day 297.
6. New-onset chronic medical conditions occurring from the time of the first study vaccination through approximately 10 months after the last study vaccination.
7. Adverse Events of Special Interest occurring from the time of the first study vaccination through approximately 10 months after the last study vaccination.

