### **9.3.4 Adverse Events of Special Interest (AESI)**

Special attention will be paid to monitoring for the occurrence of certain adverse events termed, “**Adverse Events of Special Interest**” or AESIs. These include inflammatory and autoimmune disorders that may potentially be related to the use of an immunostimulatory adjuvant (although none have been associated with the use of Na-GST-1 in combination with either AP 10-701 or CpG 10104). The occurrence of the following AESI’s will be closely monitored:

- Neuroinflammatory disorders (optic neuritis, multiple sclerosis, demyelinating disease, transverse myelitis, Guillain-Barre syndrome, myasthenia gravis, encephalitis, neuritis, Bell’s palsy)
- Musculoskeletal disorders (systemic lupus erythematosus, cutaneous lupus, Sjogren’s syndrome, scleroderma, dermatomyositis, polymyositis, rheumatoid arthritis, juvenile rheumatoid arthritis, polymyalgia, rheumatica, reactive arthritis, psoriatic arthropathy, ankylosing spondylitis, spondylarthropathy)
- Gastrointestinal disorders (Crohn’s disease, ulcerative colitis, celiac disease)
- Metabolic diseases (autoimmune thyroiditis, Grave’s or Basedow’s disease, Hashimoto thyroiditis, insulin-dependent diabetes mellitus, Addison’s disease)
- Skin disorders (psoriasis, vitiligo, Raynaud’s phenomenon, erythema nodosum, autoimmune bullous skin diseases)
- Others (autoimmune hemolytic anemia, idiopathic thrombocytopenic purpura, antiphospholipid syndrome, temporal arteritis, Behcet’s syndrome, pernicious anemia, autoimmune hepatitis, primary biliary cirrhosis, primary sclerosing cholangitis, autoimmune glomerulonephritis, autoimmune uveitis, autoimmune cardiomyopathy, sarcoidosis, Stevens-Johnson syndrome).
- Vasculitides

In addition, disorders that may potentially be related to experimental hookworm infection will be defined as AESIs that will be closely monitored following CHHI, including:

- Gastrointestinal disorders (Crohn’s Disease, Ulcerative Colitis, Irritable Bowel Syndrome)
- Gastrointestinal bleeding
- Anemia (greater than Grade 1 low absolute hemoglobin concentration as defined in **Table 5**)
- Pneumonitis

The new onset of AESI’s during the study will be reported to the Sponsor, the DMID Medical Monitor, and the FDA in the same fashion as described above in **Section 9.3.1** for SAEs.

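### Participants left untreated at Day 280 stay in this trial to Day 380 with no scheduled blood count after Day 297, and at Day 297 only if eosinophilic, despite the commitment to regular counts throughout infection

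*Protocol*

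**What the plan says.** Protocol 7.8 states that donor sub-study entrants forgo the Day 280 treatment: "Participants will not receive the 3-dose treatment of albendazole 400 mg scheduled at Study Day 280, but will be permitted to remain infected". The same section sets 6 years as the first limit on how long that may last. They remain in this trial until Visit 39 (Day 380), and "Participants will complete all study procedures described in Sections 7.3 and 7.4". Section 7.8 adds HIV and hepatitis tests for donors but no hemoglobin. Separately, a positive pregnancy test at Day 280 blocks albendazole (7.3), and treatment is then deferred until after the first trimester (7.7, 9.3.6).

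On monitoring, Section 2.3.2 commits as follows: "Subjects will be monitored throughout their infection for the development of anemia, by means of regular complete blood counts". It adds that significant anemia meeting a halting rule will be treated with albendazole.

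Section 9.3.4 lists, among the events of special interest (AESIs) after controlled human hookworm infection (CHHI), "Anemia (greater than Grade 1 low absolute hemoglobin concentration as defined in" (the reference is to Table 5). AESIs are collected to Day 380 (9.4), and a primary safety outcome in 3.2.1 is "Frequency of Adverse Events of Special Interest through approximately 10 months after the third study vaccination". Under 9.5, a single AESI judged at least possibly related to vaccine or CHHI meets a halting rule.

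For Day 280, Section 7.3 says "Obtain blood for hematology, antibody and cellular assays". At Day 297 hematology is limited to subjects with post-CHHI eosinophilia. Day 320 (7.3) and Day 380 (7.4) list antibody and, at Day 320, autoimmune serology, but no hematology.

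**The concern.** The visits after Day 280 suit people who have been cured. Section 7.8 applies them unchanged to people the protocol chooses to leave infected. Frequent hemoglobin checks stop at the planned treatment date, but for these participants the worms remain.

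What is at stake is the safety of those individuals. The Section 2.3.2 safeguard, albendazole for significant anemia that meets a halting rule, works only if the anemia is found, and the AESI is defined by a laboratory value. After the last count, a fall in hemoglobin comes to light only if history or examination prompts a test (7.6, 8.2.1).

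**Working it through.** **1. Reproduce the plan's blood volume, to confirm which visits include a CBC.** Tube volumes in Appendix A: CBC 2 mL, ALT/creatinine 5, RF/anti-dsDNA 5, antibody 10, cellular 50. The vaccination phase totals 604 mL. The CHHI-phase visits are:

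67 + 10 + 67 + 62 + 62 + 2 + 2 + 62 + 2 + 2 + 62 + 62 + 15 + 10 = 487 mL

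604 + 487 = 1091 mL, which matches Section 7 and Appendix A. The late visits break down as:

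| Day | Components (mL) | Visit | Running total | CBC included |
|---|---|---|---|---|
| 280 | 10 + 50 + 2 | 62 | 1004 | yes |
| 297 | 10 + 50 + 2 | 62 | 1066 | eosinophilia only |
| 320 | 10 + 5 | 15 | 1081 | no |
| 380 | 10 | 10 | 1091 | no |

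The volumes agree with the visit text in 7.3 and 7.4: neither Day 320 nor Day 380 has room for the 2 mL CBC.

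**2. Count intervals before treatment.** Hematology days in 7.3 from CHHI: 140, 154, 175, 189, 203, 217, 231, 245, 259, 280. That is 10 counts, with gaps of 14, 21, 14, 14, 14, 14, 14, 14 and 21 days. The maximum is 21.

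**3. Interval afterwards for a donor, to Day 380.**
- With eosinophilia (last count Day 297): 380 − 297 = 83 days.
- Without (last count Day 280): 380 − 280 = 100 days.
- Time from CHHI to Day 380: 380 − 140 = 240 days, so 83/240 = 35% and 100/240 = 42%.
- Against the longest earlier gap: 83/21 = 4.0 and 100/21 = 4.8 times.

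These are nominal days. For a participant deferred for pregnancy the untreated gap ends when albendazole is given, so it need not reach 83 or 100 days.

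**4. Intervals with the proposed counts.** 297 − 280 = 17; 320 − 297 = 23; 380 − 320 = 60 days. Added volume: 2 × 2 = 4 mL, giving 1095 mL. The Day 297 tube is already in the 1091 mL.

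**The case against.** The strongest reply is that donors enroll under another protocol, SVI-CH-01, where they may have their own hemoglobin monitoring; Section 2.1.9.1 says existing donors are followed monthly. This stands as a limit. A reader might infer that donors have no hemoglobin monitoring at all, and the documents do not support that. They show only that this protocol schedules none, cites none, and provides no route for such results into its safety data. Nor would donor monitoring obviously cover a participant deferred for pregnancy.

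A reader might also see separate contradictions in Section 8.2.1 ("CBC parameters will be assessed for safety throughout the trial") and Section 9.1 ("Clinical safety laboratory adverse events occurring throughout the study"). They are not. The first names which CBC parameters count, the second names a class of event, and neither sets a frequency. If either required counts to Day 380, the schedule would breach it for treated subjects too. Only Section 2.3.2 is tied to the duration of infection. It cannot sensibly bind this trial for a six-year donor infection, but it can for the days to Visit 39.

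A third inference is that the primary safety comparison is compromised. It is not: late counts are absent from the schedule in every arm. Adding them only for the untreated would tie detection to infection status, and if a vaccine works, infected donors would come mostly from placebo. That limits how the added counts may be used, but it does not remove the reason to take them.

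The hemoglobin margin is also easy to overstate. From the lowest value allowed at entry (5.2), a fall of 11.1 − 10.2 = 0.9 g/dL in women or 12.5 − 10.9 = 1.6 g/dL in men reaches Grade 2 (Table 5). The relevant starting point is Day 280, after ten counts, when someone near the threshold would already be visible.

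Finally, discretionary tests exist (7.6, 8.2.1), and history and examination continue at Days 320 and 380. These help, but they are not regular counts.

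**Conclusion.** The point holds as a gap between a stated safety commitment and the schedule that should deliver it. A donor goes 83 days (eosinophilic) or 100 days (not) without a scheduled CBC while infected and still in this trial. The 83-day figure is the likelier for infected donors, because 9.5 exempts post-CHHI eosinophilia from a halting rule and so evidently expects it.

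The likelihood of harm is low. The challenge is 50 larvae, against 40 to 160 adult worms for anemia-causing blood loss (2.1.1). Iron deficiency is excluded at entry (5.2), and counts have been frequent up to Day 280. The number of donors is not stated and may be zero; in the earlier study 2 of the 10 in the 50-larvae cohort became donors (2.1.9.1).

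The conclusion rests on Sections 7.3, 7.4 and 7.8 as written and assumes nothing about SVI-CH-01. The flotation endpoint and the Week 5 to 20 egg counts are unaffected. The change is worth making because it is cheap and serves individual safety.

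**What to change.** In Sections 7.3 and 7.4 and Appendix A, for any participant still untreated after Day 280, make the Day 297 CBC unconditional and add a 2 mL CBC at Visits 38 and 39. Both visits already draw blood. If SVI-CH-01 already measures donor hemoglobin on comparable dates, say so in 7.8 instead and bring those results into this trial's safety data; pregnancy deferrals would still need the added counts.

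State in the SAP that these late counts are descriptive and are not compared across arms. SAP 5.7.5.1 tests adverse event frequencies between groups, so an anemia found only through an added count should be identifiable. A separate listing of untreated participants is optional, since SAP 5.7.5 and 5.7.5.6 already list safety data by subject. The statement in Protocol 2.3.1.3 that prolonged infection will not occur in this study deserves a wording edit.

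Cost: 4 mL more blood per untreated participant (1091 to 1095 mL), no new visit, and short text changes. A 60-day interval between Visits 38 and 39 remains.

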## 8 STUDY PROCEDURES/EVALUATIONS

### 8.1 Clinical Evaluations

Subjects will be monitored for local and systemic adverse events during specific protocol-defined periods. As with other aluminum hydroxide-adsorbed vaccines, hypersensitivity reactions would be expected to occur within the first 24 hours after vaccination, and other severe local or systemic reactions within 72 hours of vaccination. Subjects will therefore be observed for immediate reactions following each vaccination for at least 1 hour, and will have a clinical assessment at the study clinic on Days 7 and 14 following each vaccination. A telephone call with the subject will take place on Days 3 and 28 following vaccinations 1 and 2 to monitor for adverse events. Day 28 following vaccination 3 falls on the day of CHHI and the subject will be assessed at the study clinic. Should a subject call on a study clinician to report an adverse event (AE), it will be fully documented in their study chart, and discussed with the Principal Investigator.

Following CHHI, local larval application site reactions are expected to occur within the first month after application of the larvae. Subjects will therefore be observed for immediate reactions following each larval application for at least 1 hour. Subjects will have a telephone call on day 3 following CHHI to monitor for adverse events. A clinical assessment at the study clinic will be performed on Days 7 and 14 following CHHI. Gastrointestinal AEs are expected to occur after approximately week 4 after CHHI; subjects will therefore be evaluated weekly from weeks 5 through 20 after CHHI, until treatment with albendazole.

All AEs will be graded for severity and relationship to study vaccine or larval application, captured on the appropriate case report form (CRF), and followed to resolution. All Serious Adverse Events (SAEs) will be reviewed by a study physician, recorded on the appropriate SAE form, reported according to applicable regulations and guidelines, and followed through to resolution or stabilization by a study clinician. Special attention will also be paid to monitoring for the occurrence of Adverse Events of Special Interest (AESIs), which include inflammatory and autoimmune disorders that may potentially be related to the use of an immunostimulatory adjuvant, and gastrointestinal, hematologic or respiratory disorders that may potentially be related to CHHI.

A DMID Medical Monitor and a local Independent Medical Monitor will be appointed and a Safety Monitoring Committee (SMC) formed to monitor subject safety and to advise the Principal Investigator and co-investigators on trial-related medical questions or problems. The SMC will periodically review data on safety and enrollment, and will review cumulative safety data for evidence of study related AEs, adherence to the protocol, and factors that may affect outcome or study data such as protocol violations and losses to follow up.

### 8.2 Laboratory Evaluations

#### 8.2.1 Clinical Laboratory Evaluations

Using standard techniques, the tests listed below will be performed at the site's clinical laboratory. One or more of the laboratory parameters may be repeated at any time during the

study as determined by the PI, if indicated by an AE. A clinically significant abnormal value should be repeated within 10 days if possible and followed up as clinically relevant.

1. Complete blood count plus white blood cell (WBC) differential\*
2. Serum creatinine
3. Alanine aminotransferase (ALT)
4. Rheumatoid factor (RF)
5. Anti-double stranded DNA antibody (anti-dsDNA)
6. HBsAg ELISA
7. HCV serology
8. HIV serology
9. Serum ferritin

*\*The following CBC parameters will be assessed for safety throughout the trial: WBC count, absolute neutrophil count, absolute eosinophil count, hemoglobin concentration and platelet count.*

Urine pregnancy testing will be performed at the clinical trial site using test kits that have been approved by the FDA. Urine dipstick testing will also be performed at the trial site using an approved product.

Parasitological and immunology assays (see below) will be performed in the laboratories of the Department of MITM at the GWU, and at Baylor College of Medicine (fecal PCR for hookworm DNA).

